3.4.1.1 Primary Analysis

The primary efficacy outcome measure is the change in the LFC (as measured by MRI-PDFF) from baseline to Week 12/ET.

The primary efficacy analysis will be performed on the ITT Population. Missing MRI-PDFF values at Week 12/ET will be imputed based on the missing at random assumption using multiple imputation. Baseline MRI-PDFF will not be imputed; it is not expected to be missing for any patients.

The multiple imputation procedure and the analysis will be conducted in three separate steps: 1) Multiple Imputation, 2) ANCOVA Model based analysis by Imputed data set, and 3) combination of results using Rubin's rule.

1. Multiple imputation (using SAS PROC MI). Since baseline is required for inclusion and there is only one post-baseline MRI assessment, the missing pattern is monotone. The imputation model will include treatment, stratification factors, and baseline LFC. Note for Part B the baseline LFC is included, and so the LFC stratification factor will not be included in the imputation model. Missing data will be imputed 100 times to generate 100 complete datasets. Sample SAS code is below.

```
*****
Part A:
    TRT01PN: 0=Placebo, 1=Pooled EYP001a
    STRAT1: T2DM (Y, N)
    STRAT2: Statin Use (Y, N)
Part B:
    TRT01PN: 0=Placebo, 1=EYP001a 100 mg QD, 2=EYP001a 200 mg QD
    STRAT1: Statin Use (Y, N)
    STRAT2: Not included
BASE: Baseline LFC
Week12: Week 12/ET LFC
*****
proc mi data=ADEFF seed=345678 n impute=100 out=midatal;
minimum=(. . . . 0) maximum=(. . . . 100);
class TRT01PN STRAT1 STRAT2;
monotone reg(WEEK12 = TRT01PN STRAT1 STRAT2 BASE /details);
var TRT01PN STRAT1 STRAT2 BASE WEEK12;
run;
```

2. Analysis of imputed datasets. Imputed datasets will be analyzed separately using the primary endpoint analysis model. The change in LFC from baseline to Week 12/ET will be analyzed using an analysis of covariance (ANCOVA) model with baseline LFC as a covariate and treatment and stratification groups as factors. Note for Part B the baseline

LFC is included as a covariate, and so the LFC stratification factor will not be included in the ANCOVA model. The least square means (LSMeans) for change from baseline to Week 12/ET LFC within the treatment groups and pairwise differences in LSMeans will be estimated along with their 95% CIs and p-values using Bonferroni method. Sample SAS code is below.

```
*****
Part A:
  TRT01PN: 0=Placebo, 1=Pooled EYP001a
  STRAT1: T2DM (Y, N)
  STRAT2: Statin Use (Y, N)
Part B:

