  TRT01PN: 0=Placebo, 1=EYP001a 100 mg QD, 2=EYP001a 200 mg QD
  STRAT1: Statin Use (Y, N)
  STRAT2: Not included
  BASE: Baseline LFC
  CHG: LFC change from Baseline to Week 12/ET
*****
proc mixed data=miout;
by _Imputation_;
class TRT01PN STRAT1 STRAT2;
model CHG = TRT01PN STRAT1 STRAT2 BASE / ddfm=KR;
lsmeans TRT01PN / COV PDIFF CL;
run;
```

3. Combination of estimates across imputed datasets (using SAS PROC MINANALYZE). This will be performed using Rubin's rule and the overall treatment estimates vs. placebo along with their two-sided 95% CI, two-sided 97.5% CI, and p-value will be provided.

```
*****
Part A: TRT01PN: 0=Placebo, 1=Pooled EYP001a
Part B: TRT01PN: 0=Placebo, 1=EYP001a 100 mg QD, 2=EYP001a 200 mg QD
*****
proc mianalyze data=lsmeans;
by TRT01PN;
modeleffects estimate;
stderr stderr;
run;
```

The primary efficacy results will subsequently be analyzed by adding LSM and CAP values at enrollment as additional covariates.

Normality assumptions will be assessed via review of residual plots and non-parametric analyses may be explored if needed.

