SHIFTPBO:  $\delta$ , such as -1 to 1 by 0.1
BASE: Baseline LFC
CHG: LFC change from Baseline to Week 12/ET
*****
proc GLM;
by _Imputation_ SHIFTEYP SHIFTPBO;
class TRT01PN STRAT1 STRAT2;
model CHG = TRT01PN STRAT1 STRAT2 BASE;
lsmeans TRT01PN / CL DIFF STDERR;
estimate "EYP001a vs Placebo" TRT01PN / 1 -1 / E;
run;

proc mianalyze data=diffs;
by SHIFTEYP SHIFTPBO;
modeleffects difference;
stderr stderr;
run;
```

Results will then be summarized using tables and a contour plot of the upper limit of 95% CI of LSMean difference between EYP001a and Placebo arms in change from baseline in LFC at Week 12/ET for the different δ will also be provided.

Then smallest value of δ EYP001a for a value of δ Placebo equal to 0 which will reverse the conclusion for the primary endpoint will be provided.

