3.4.1.4 Key Secondary Analysis: Percent Change

The main analysis of percent change from baseline will be performed on the ITT Population. As for the primary analysis, missing MRI-PDFF values at Week 12/ET will be imputed based on the missing at random assumption using multiple imputation.

The percent change from baseline to Week 12/ET in LFC will be analyzed for the ITT Population in similar ANCOVA model as described for the primary analysis. The analysis will be repeated as sensitivity analyses for the mITT and Per-Protocol Populations.

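### The step 3 pooling code for the primary analysis does not produce the dose-versus-placebo estimate, confidence intervals and p-value that the SAP text promises

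*SAP*

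**What the plan says.** Protocol 10.2.1.1 bases the primary result on pairwise comparisons of each EYP001a dose with placebo from the ANCOVA. SAP 3.1.7 describes two Part B tests, each dose against placebo, with Bonferroni control at one-sided 0.025.

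SAP 3.4.1.1 implements this in three steps.

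- **Step 2, text:** LS means are estimated within each group, and "pairwise differences in LSMeans will be estimated along with their 95% CIs and p-values using Bonferroni method".
- **Step 2, code:** "lsmeans TRT01PN / COV PDIFF CL". This requests arm means and all pairwise differences, with no control level named.
- **Step 3, text:** "the overall treatment estimates vs. placebo along with their two-sided 95% CI, two-sided 97.5% CI, and p-value will be provided".
- **Step 3, code:** "proc mianalyze data=lsmeans", by TRT01PN, with "modeleffects estimate" and the matching standard error. The coding key above it lists placebo as level 0 and, for Part B, the two doses as levels 1 and 2.

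SAP 3.4.1.2 repeats the primary analysis under the tipping-point method. Its pooling code is "proc mianalyze data=diffs", with the difference as the model effect.

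For LFC percent change, SAP 3.4.1.4 says that the endpoint "will be analyzed for the ITT Population in similar ANCOVA model as described for the primary analysis". SAP 3.4.1.5 makes a similar reference for cT1.

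**The concern.** The text and the code of step 3 describe different quantities. The text asks for a contrast with placebo. On its face, the code pools each arm's own adjusted mean, and PROC MIANALYZE tests a pooled effect against zero unless told otherwise. The hypothesis tested is then that the arm did not change from baseline.

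This is the only pooling code printed for the primary p-value and intervals. Every arm receives diet and lifestyle counselling (Protocol 9.14), so some improvement on placebo is plausible. If within-arm p-values were reported as the comparison, that shared improvement would enter the result and the randomised contrast would drop out.

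Timing adds to the risk. SAP 4.2 puts topline output about one week after first lock and unblinding, so a correction made at that stage would be made with results in view.

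**Working it through.** **1. The plan's own figure.** Protocol 10.2.8 and SAP 2.2.4 assume a difference of 5.1, SD 5.8, one-sided alpha 0.0125 per dose and power 0.80. The normal quantiles are 2.2414 and 0.8416.

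- n per arm = 2 × [5.8 × (2.2414 + 0.8416) / 5.1]² = 24.6, so 25 by the Z-test.
- At n = 26 the Z-test power is 0.824. A t-test needs exactly 26 (power 0.802).
- 26 / 0.87 = 29.9, so 30 randomised per arm.

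The stated 26 and 30 are reproduced to within one patient. The trial is sized for a between-arm test.

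**2. Can the step 3 code give that test?**

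- *If the pooled data set holds LS means:* the BY groups are the arms. Part B gives three rows, one of them placebo, each tested against zero.
- *If it holds the pairwise-difference table under another name:* in Part B, all-pairs output sorted by TRT01PN puts 0-versus-1 and 0-versus-2 in one BY group and 1-versus-2 in another. The two dose contrasts would be pooled as if they were imputations of a single quantity. In two-group Part A this reading gives one valid contrast with its sign reversed.
- *If it holds differences already filtered to dose minus placebo:* the code works, but no such step is shown.

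No alpha option is set, so the promised 97.5% interval is not requested on any reading.

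**3. Consequence if the code is run unchanged and the active-arm rows are reported.** Suppose there is no drug effect and every arm has the same true change d. Then

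P(own-arm one-sided p < 0.0125) = Φ(|d| / (5.8/√n) − 2.2414).

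With n = 26, 5.8/√26 = 1.137.

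| Shared change d | Source | Per dose, n = 26 | Per dose, n = 30 |
|---|---|---|---|
| 0 | reference | 0.0125 | 0.0125 |
| -0.9 | placebo value that Protocol section 1 cites from a 12-week study of another drug | Φ(0.791 − 2.2414) = 0.074 | 0.082 |
| -2 | assumed | 0.315 | 0.362 |
| -3 | assumed | 0.654 | 0.723 |

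For at least one of two doses at d = -0.9, treating the arms as independent: 1 − (1 − 0.074)² ≈ 0.14, against a family-wise target of 0.025.

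**4. Simulation check.** Two simulations of Part B used 30 per arm, about 13% missing at random, residual SD 5.8, regression imputation, ANCOVA and Rubin's rules. At d = -0.9:

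- Own-arm rejection per active arm was 7.3% in one simulation (3,000 trials, 40 imputations), and 6.8% and 7.4% for the two doses in the other (2,000 trials, 20 imputations).
- Rejection for any dose was 13.9% and 13.6%.
- In the second simulation the placebo row was itself significant in 7.6% of trials.

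Pooling dose-minus-placebo differences instead gave 1.0% to 1.8% per dose for every d from 0 to -3. Power was about 0.80 per dose at a true difference of 5.1, as planned.

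**The case against.** The strongest reply is that the governing text is right and is repeated. Protocol 10.2.1.1, SAP 3.1.7 and the prose of steps 2 and 3 all specify each dose against placebo. The tipping-point section presents itself as a repeat of the primary analysis and pools differences, which supports a between-arm intention.

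The code is also plainly incomplete. Steps 1 and 2 call it sample code. Step 1 writes a data set named midatal and step 2 reads one named miout. Week 12 LFC is imputed but change is modelled, with no derivation shown. No ODS OUTPUT statement appears, so the contents of the pooled data set are inferred from its name. SAP section 6 leaves detail to separate programming specifications. Step 2 also asks for within-arm LS means, so pooling them by arm could be a legitimate descriptive step, with a second call for the differences left out.

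All of this stands, and it rules out a stronger reading. A reader might infer from the code that the trial plans a within-arm primary test and will count a shared improvement as a drug effect. The documents do not support that: the stated comparison is with placebo throughout, and a placebo row with its own p-value would appear in the output.

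The reply does not remove the contradiction. No printed code for the primary analysis yields the promised contrast without an unshown step, and neither section 5 nor section 6 of the SAP corrects it.

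**Conclusion.** The step 3 code does not compute the estimate, intervals and p-value that the sentence above it promises. This is a text-code contradiction at the primary analysis, to be corrected before database lock. It is not a flaw in the planned comparison.

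The error rates in the working are conditional. They apply only if the code is run as printed and the active-arm rows are reported as the drug effect. Under that condition, the per-dose error at a shared change of -0.9 is about six times nominal (7.4 / 1.25). They rest on the plan's SD of 5.8 and 26 patients per arm. The -0.9 comes from another drug's trial, and the larger shared changes are assumptions. The simulations further assumed a baseline LFC distribution, 50% statin use and missingness unrelated to outcome.

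The reach to LFC percent change and cT1 is also conditional. Those sections carry over the imputation approach and a similar model, but they do not cite the pooling code.

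**What to change.** In step 2, request and save dose-minus-placebo differences: `lsmeans TRT01PN / PDIFF=CONTROL('0') CL;` with `ods output Diffs=diffs;`.

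In step 3, sort that data set by TRT01PN and _Imputation_, then run PROC MIANALYZE on it by TRT01PN, keeping the existing model-effect and standard-error lines. In Part B the BY levels are then 1 and 2 only, each being that dose minus placebo. Run it at alpha=0.05 and alpha=0.025 for the 95% and 97.5% intervals.

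Keep the pooled arm LS means as descriptive output without p-values. Apply the same pooling step wherever LFC percent change and cT1 reuse the primary procedure.

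The cost is a few lines in the SAP sample code and a check that the programming specifications match. No data, patients or timelines are affected.

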3.4.1.2 Sensitivity Analysis

Sensitivity analyses will be conducted by repeating the primary efficacy analysis based on:

- The ITT Population with missing MRI-PDFF values at Week 12/ET imputed using the multiple imputation with tipping point method based on the missing not at random assumption (further details provided below)
- The mITT Population

- The Per-Protocol Population

Tipping-point analysis

Robustness of the primary analysis results to the departure from the MAR assumption will be explored in the ITT population using the tipping-point analysis based on the pattern mixture model approach.

The considered pattern mixture model will introduce a penalty δ corresponding to the difference in mean change from baseline to Week 12/ET LFC between patients with missing data and patients with observed data.

Estimations will be performed using the same MI approach as described previously. In each treatment group, a penalty δ will be added to the imputed values ($\delta = 0$ corresponds to the MAR assumption) after the PROC MI step. Sample SAS code is below.

```
*****
Part A:
    TRT01PN: 0=Placebo, 1=Pooled EYP001a
    STRAT1: T2DM (Y, N)
    STRAT2: Statin Use (Y, N)
Part B:
    TRT01PN: 0=Placebo, 1=EYP001a 100 mg QD, 2=EYP001a 200 mg QD
    STRAT1: Statin Use (Y, N)
    STRAT2: Not included
&Shifti:  $\delta$ , such as -1 to 1 by 0.1
&Shiftj:  $\delta$ , such as -1 to 1 by 0.1
BASE: Baseline LFC
CHG: Change from Baseline to Week 12/ET LFC
*****
proc mi data=ADEFF seed=345678 n impute=100 out=midatal;
minimum=(. . . . -100) maximum=(. . . . 100);
class TRT01PN STRAT1 STRAT2;
monotone reg;
mnar adjust(CHG / shift=&Shiftj adjust=(TRT01PN='1'))
    adjust(CHG / shift=&Shifti adjust=(TRT01PN='0'));
var TRT01PN STRAT1 STRAT2 BASE CHG;
run;
```

To investigate how the conclusions depend on the adopted values δ , the testing will be repeated over a range of plausible values for the pairs (δ pooled EYP001a, δ Placebo for Part A; δ each EYP001a group, δ Placebo for Part B). The δ values range from -1 to 1 by 0.1, in each treatment group. The δ values may be adjusted depending on the actual data observed. Sample SAS code is below.

```
*****
Part A:
    TRT01PN: 0=Placebo, 1=Pooled EYP001a
    STRAT1: T2DM (Y, N)
    STRAT2: Statin Use (Y, N)
Part B:
    TRT01PN: 0=Placebo, 1=EYP001a 100 mg QD, 2=EYP001a 200 mg QD
    STRAT1: Statin Use (Y, N)
    STRAT2: Not included
```

```
SHIFTEYP:  $\delta$ , such as -1 to 1 by 0.1
SHIFTPBO:  $\delta$ , such as -1 to 1 by 0.1
BASE: Baseline LFC
CHG: LFC change from Baseline to Week 12/ET
*****
proc GLM;
by _Imputation_ SHIFTEYP SHIFTPBO;
class TRT01PN STRAT1 STRAT2;
model CHG = TRT01PN STRAT1 STRAT2 BASE;
lsmeans TRT01PN / CL DIFF STDERR;
estimate "EYP001a vs Placebo" TRT01PN / 1 -1 / E;
run;

proc mianalyze data=diffs;
by SHIFTEYP SHIFTPBO;
modeleffects difference;
stderr stderr;
run;
```

Results will then be summarized using tables and a contour plot of the upper limit of 95% CI of LSMean difference between EYP001a and Placebo arms in change from baseline in LFC at Week 12/ET for the different δ will also be provided.

Then smallest value of δ EYP001a for a value of δ Placebo equal to 0 which will reverse the conclusion for the primary endpoint will be provided.

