3.1.5 Absolute Change and Relative Change

Change (absolute) from baseline will be derived for each analysis visit as visit value minus baseline.

Percent (relative) change from baseline will be derived for each analysis visit as $[(\text{visit value} - \text{baseline})/\text{baseline}] \times 100$.

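### The tipping-point sample code computes placebo minus EYP001a under the opposite label, and gives the Part B 200 mg arm neither a contrast nor a delta

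*SAP*

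**What the plan says.** SAP 3.4.1.2 describes a pattern-mixture tipping-point analysis in the ITT Population. A penalty delta is added to the imputed values in each treatment group, the ANCOVA is refitted over a grid of deltas, and the results are combined by Rubin's rule. For Part B the text promises delta pairs for each EYP001a group against placebo.

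The code comments define the treatment variable for Part A as "TRT01PN: 0=Placebo, 1=Pooled EYP001a" and for Part B as "TRT01PN: 0=Placebo, 1=EYP001a 100 mg QD, 2=EYP001a 200 mg QD". The model step declares "class TRT01PN STRAT1 STRAT2" with no ordering or reference option. It asks for differences in two ways: "lsmeans TRT01PN / CL DIFF STDERR" and "estimate 'EYP001a vs Placebo' TRT01PN / 1 -1 / E". The pooling step, "proc mianalyze data=diffs", reads a variable called `difference` and is run by `SHIFTEYP` and `SHIFTPBO` only.

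The planned display is a "contour plot of the upper limit of 95% CI of LSMean difference between EYP001a and Placebo arms". The SAP also asks for the smallest EYP001a delta, with the placebo delta at 0, that overturns the primary conclusion. The sign of the outcome is fixed in SAP 3.1.5: "Change (absolute) from baseline will be derived for each analysis visit as visit value minus baseline". A fall in liver fat is therefore negative, and benefit is a negative EYP001a minus placebo difference.

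**The concern.** The upper limit shows whether the benefit survives only if the difference is EYP001a minus placebo. The contrast carries that label, but its coefficients appear to run the other way. The same template is offered for Part B, which SAP Section 1 names as the SAP's focus. Part B has three treatment levels, yet the contrast has two coefficients and the delta step shifts only two levels.

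The tipping-point analysis is the only planned check of the primary result that departs from missing at random, and Protocol 10.2.1.2 commits to it as well. Followed literally, the code could plot the wrong confidence limit and leave one of the two Part B doses out of the check.

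**Working it through.** **1. The plan's own figure (inputs for the illustration).** Protocol 10.2.8 and SAP 2.2.4 give a difference of 5.1, SD 5.8, one-sided alpha 0.0125 per comparison, power 0.8, 26 completers and 30 randomized per group.

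- Z-test: n = 2 x [5.8 x (2.2414 + 0.8416) / 5.1]^2 = 24.6, so 25.
- A t-test gives 26 (power 0.802). The stated 26 is reproduced to within one patient.
- 26 / 0.87 = 29.9, so 30.

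**2. Direction of the contrast.** In default ascending order the class levels are 0, 1 (and 2 in Part B). Coefficients `1 -1` weight level 0 by +1, level 1 by -1 and level 2 by 0.

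- Part A: placebo minus pooled EYP001a.
- Part B: placebo minus 100 mg. The 200 mg group does not enter.

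**3. Effect on the plotted limit.** SE = 5.8 x sqrt(2/26) = 1.609, and 1.96 x 1.609 = 3.153.

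| Difference | Estimate | 95% CI | Upper limit |
|---|---|---|---|
| EYP001a minus placebo (intended) | -5.1 | -8.25 to -1.95 | -1.95 |
| Placebo minus EYP001a (as coded) | +5.1 | 1.95 to 8.25 | +8.25 |

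The coded upper limit is minus the intended lower limit.

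**4. Check with imputed data.** One artificial Part B data set was used: 30 per arm, 4 missing per arm (13% of 30), observed effect set to 5.1, residual SD set to 5.8, 100 imputations, Rubin's rule. Delta was added to the imputed 100 mg values, with the placebo delta at 0.

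| EYP001a delta | As coded (95% CI) | Intended (95% CI) |
|---|---|---|
| -1 | 5.24 (2.04 to 8.43) | -5.24 (-8.43 to -2.04) |
| 0 | 5.11 (1.92 to 8.30) | -5.11 (-8.30 to -1.92) |
| 1 | 4.98 (1.78 to 8.17) | -4.98 (-8.17 to -1.78) |

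The two-sided p at delta 0 is 0.0017 in both directions. Taking tipping as the first delta at which the interval includes 0, the tipping delta is also the same in both directions: about 12.9 with a 95% interval and about 10.0 with a 97.5% interval. Delta is added before the contrast is formed, so reversing the contrast cannot move it.

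**5. Coverage of Part B.** The text promises deltas for each EYP001a group. The code shifts treatment level '1' and level '0' only, so imputed 200 mg values stay at missing at random whatever the grid.

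**6. Pooling.** The SAP does not show how `diffs` is built. If it came from the LSMEANS differences, the default direction would again be lower level minus higher level, and Part B would have three rows per imputation. With no contrast name among the BY variables, Rubin's rule would combine all three. With both doses at the planning effect the rows average (5.1 + 5.1 + 0) / 3 = 3.4. The spread between rows is (1.7^2 + 1.7^2 + 3.4^2) / 3 = 5.78, so SE = sqrt(1.609^2 + 5.78) = about 2.9. The intended result is 5.1 with SE 1.6 for each dose; 3.4 estimates the effect of neither.

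**The case against.** The block is introduced as sample code and is plainly schematic: the model step names no input data set and no step creates `diffs`. The slash before the coefficients would stop the contrast line running as printed, though it may come from the PDF conversion. SAP Section 6 leaves detailed programming specifications to other documents. The text names the EYP001a and placebo difference, and SAP 3.1.1 has the Part B groups analysed separately. A competent programmer might correct the sign and rerun the template with level 2 in place of level 1. It is not shown that the ESTIMATE line feeds the plot at all. All of this stands. It makes the wrong plot and the mixed pooling risks rather than certainties.

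It does not remove the defect. Both visible candidate sources for `diffs` run placebo minus EYP001a by default, and nothing in the SAP flips the sign, supplies the 200 mg contrast or adds the missing delta.

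A reader might go further and infer that the tipping delta is reversed too, so that robustness would be overstated several-fold. Holding the SE fixed with 13% imputed, the intended limit would reach 0 at 1.95 / 0.13 = 15 points and the reversed one at 8.25 / 0.13 = about 63. The documents do not support this:

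- The SAP defines tipping as a reversal of the primary conclusion, and whether the interval includes 0 is the same in either direction (step 4).
- Anyone requiring the upper limit to be below 0 would see the reversed contrast fail at delta 0, so the error would show at once.
- The SE does not stay fixed. Shifting 4 of 30 values in one arm by 63 adds about 0.133 x 0.867 x 63^2 / 3 = 153 to a residual variance of 33.6, which more than doubles the SE.

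**Conclusion.** Wrong as written, and confined to the sample code of a sensitivity analysis. The contrast contradicts its label. Plotted unchanged, its upper limit would be about +8.25 where about -1.95 is meant. For Part B the template gives the 200 mg dose no contrast and no delta, although the text promises both doses, and the pooling step cannot keep contrasts apart if `diffs` holds more than one.

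This rests on default class ordering, on the coefficients being read without the stray slash, and on the planning values for the size. The figures from the artificial data set are illustrations, not predictions. The size of the tipping delta is not in question, and the primary analysis is not affected because its separate PROC MIXED code does not use this contrast.

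**What to change.** In SAP 3.4.1.2:

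- Part A: use `TRT01PN -1 1`, labelled EYP001a minus placebo.
- Part B: use two statements, `TRT01PN -1 1 0` (100 mg minus placebo) and `TRT01PN -1 0 1` (200 mg minus placebo).
- Remove the slash before the coefficients if it is in the source file.
- Add a delta adjustment for `TRT01PN='2'`.
- Show how `diffs` is built from these contrasts, and add the contrast name to the BY list in PROC MIANALYZE so that each dose is pooled and plotted separately.
- State in the text that the plotted difference is EYP001a minus placebo.

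The cost is a few lines of sample code and one sentence. No design, data collection or primary analysis changes.

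### The Part B tipping-point contour is drawn at the 95% confidence limit, although each Part B dose is tested at one-sided 0.0125

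*SAP*

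**What the plan says.** SAP 3.1.7 applies Bonferroni to the two Part B comparisons at a family-wise one-sided 0.025. Protocol 10.2.8 and SAP 2.2.4 give the resulting 0.0125 per dose. Part A has a single pooled comparison and no adjustment. Step 3 of SAP 3.4.1.1 reports a two-sided 97.5% CI as well as a 95% CI.

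SAP 3.4.1.2 opens: "Sensitivity analyses will be conducted by repeating the primary efficacy analysis based on" several alternatives, one of them the tipping-point analysis. On the shifts it says "the testing will be repeated over a range of plausible values for the pairs", written for Part B as "δ each EYP001a group, δ Placebo for Part B". It also says "The δ values range from -1 to 1 by 0.1, in each treatment group", and then "The δ values may be adjusted depending on the actual data observed". The code headers give the same grid as an example ("such as -1 to 1 by 0.1").

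Two outputs follow. One is a "contour plot of the upper limit of 95% CI of LSMean difference between EYP001a and Placebo arms", with no separate level for Part B. The other is the smallest active-arm delta, with placebo delta at 0, that overturns the primary conclusion.

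The sample MNAR statement begins "mnar adjust(CHG / shift=&Shiftj adjust=(TRT01PN='1" and has a second adjustment for code 0. The header codes 200 mg as 2, and code 2 has no adjustment.

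**The concern.** A tipping-point plot is read by asking where the upper confidence limit reaches zero. If the limit is less strict than the test, part of the region shown as still favourable is a region where the tested conclusion has already been lost. In Part B the plot uses 1.960 standard errors and the test uses 2.241.

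This is the only missing-not-at-random check on the continuous primary endpoint, and the error runs in the flattering direction. The tipping delta is defined by the primary conclusion and so takes the stricter level. The plot and the delta can therefore give different answers within one section.

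Two smaller matters sit beside it. The sample code does not do what the prose asks for 200 mg. And the stated grid is too narrow to reach the tipping delta that the section asks for, with no rule for extending it.

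**Working it through.** **Inputs.** Difference 5.1, SD 5.8, one-sided 0.0125 per dose, power 0.8, 26 completers and 30 randomized per arm (SAP 2.2.4, Protocol 10.2.8); 100 imputations (SAP 3.4.1.1). Assumption: m = 4 of 30 scans missing per arm, from the planned 13% dropout. No gain from the baseline covariate is taken.

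**The plan's own figure.** n = 2 × 5.8² × (2.2414 + 0.8416)² / 5.1² = 24.6, so 25 per arm against the stated 26. Power at 26 is 0.824, and 26 / 0.87 = 29.9, so 30 randomized. The planning figures reproduce closely. The value 2.2414 is also the final boundary in Protocol Table 6, and it corresponds to a two-sided 97.5% CI.

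**Standard error after imputation.** Let f = m/30, and let k be the number of arms shifted by δ.

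- Within: W = (2/30) × [5.8² × 87 + k × 30 × f(1−f) × δ²] / 87
- Between: B = 2f² × 5.8² × [1/(30−m) + 1/m]
- Total: T = W + 1.01B

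With m = 4 and δ = 0: W = 2.243, B = 0.345, T = 2.591, SE = 1.610.

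**Boundaries.** The observed reduction versus placebo must exceed:

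- at 97.5%: 2.2414 × 1.610 = 3.61
- at 95%: 1.960 × 1.610 = 3.15

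The gap is 0.45.

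**What the stated grid can do.** A shift of +1 in one active arm moves the difference by 4/30 = 0.13. The worst corner (+1 active, −1 placebo) moves it by 8/30 = 0.27 and raises the SE slightly, to 1.611. There the upper limit crosses zero if the observed reduction is below:

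- at 95%: 0.267 + 1.960 × 1.611 = 3.42 (3.43 if the other dose is shifted too)
- at 97.5%: 0.267 + 2.2414 × 1.611 = 3.88

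A significant dose already exceeds 3.61, so at 95% no significant dose can cross zero anywhere on the grid. At 97.5%, doses observed between 3.61 and 3.88 do reverse.

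**How often.** With a true difference of 5.1, the share of significant results reversed at that corner on the 97.5% limit is:

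| Missing per arm | Significance boundary | Corner boundary at 97.5% | Share reversed |
|---|---|---|---|
| 4 of 30 | 3.61 | 3.88 | 5.7% |
| 2 of 30 | 3.48 | 3.61 | 2.5% |
| 1 of 30 | 3.41 | 3.48 | 1.1% |

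A simulation with full multiple imputation (3,000 trials, 100 imputations each, 4 of 30 missing) gave 2,468 significant results. The corner reversed 6.1% of them at 97.5% and none at 95%.

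**If the grid is extended.** Solve −5.1 + fδ + crit × √T = 0 with m = 4 and one arm shifted. The tipping delta is 9.9 at 97.5% and 12.7 at 95%. Both lie far outside −1 to 1.

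**Code against prose.** The prose requires a shift in every group. The sample shifts codes 1 and 0 only. The ESTIMATE line has two coefficients for three groups, and MIANALYZE is run by the shift variables but not by dose.

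**The case against.** The strongest reply is that the quantity answering the robustness question is already at the right level. The tipping delta is tied to the primary conclusion, the section repeats the testing, and results are also tabulated. Only one figure is at 95%, in line with the general reporting rule in SAP 3.1.7. This stands, and it narrows the point to the plot. It does not remove it: a figure meant to show where a conclusion fails should use the level of that conclusion.

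The size can also be challenged. Four missing scans per arm equates dropout with a missing scan. Patients who stop after at least 4 weeks on drug have an early-termination scan (Protocol 6.5), which counts as observed (SAP 3.1.4, 3.2.4), and SAP 3.1.9 expects few missing data. This stands too, which is why the shares for 2 and 1 missing are given. Even with 4 missing, about 94% of significant results are unreversed at that corner at either level.

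A reader might infer more than the documents support:

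- *That no delta range is given.* A range and a step are stated. What is absent is a rule for extending them.
- *That 200 mg will be left at missing-at-random.* The code is labelled as a sample and is shared by both parts. The prose requires a shift for each dose, LSMEANS does request pairwise differences, and SAP 6 puts detailed specifications in separate documents.
- *That the plot both hides every reversal and yields a delta about 1.3 times too large.* These need different grids: the first holds on −1 to 1, the second only on an extended grid and at an observed effect of 5.1.

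**Conclusion.** The contour level is wrong as written for Part B and right for Part A. On the stated grid at planning values, the 95% plot cannot show a reversal for any dose significant at 0.0125. This holds for up to 7 of 30 missing per arm at SD 5.8 (boundary 3.84 against a corner of 3.83), and at 4 of 30 for a residual SD above about 3.5.

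What the plot would miss at the worst corner is modest: about 6% of significant results with 4 of 30 missing, and 1% to 2.5% with 1 or 2. On an extended grid, the 95% contour would put the tipping point at 12.7 instead of 9.9 for an observed effect of 5.1; the ratio of the two changes with the observed effect.

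The sample code needs correcting to match the prose. The grid is a matter for improvement: it moves the difference by only 0.13 to 0.27 points, so at the planned effect it cannot reach the tipping delta that the section asks for. Nothing here touches the primary test, its alpha or the sample size.

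**What to change.** (a) In SAP 3.4.1.2, draw the Part B contours one per dose, and judge reversal, on the upper limit of the two-sided 97.5% CI. Keep 95% for Part A.

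(b) In the sample code, add a separate shift for TRT01PN = 2, and estimate and combine each dose versus placebo separately, running MIANALYZE by dose.

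(c) Optional: state in advance that the active-arm delta is extended upward, with placebo delta at 0, until the conclusion reverses or a pre-stated plausibility cap is reached. Report no reversal up to the cap where that applies. A cap helps because with 2 of 30 missing the tipping delta at the planned effect is already 16.5 to 19.0, depending on how many arms are shifted.

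The cost is a change of SAP wording, one more shift parameter and a longer loop. Robustness may look weaker than it would on the 95% plot.
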